5 SELECTION AND EARLY TERMINATION OF SUBJECTS

5.1 Inclusion Criteria

Subjects who meet all of the following criteria will be eligible to participate:

- 1. Subject is willing and able to provide written informed consent.
- 2. Male or female aged ≥ 18 years of age at the Screening Visit/Visit 1.
- 3. Subject has been undergoing treatment for primary ITP with eltrombopag or romiplostim for at least 90 days prior to the Screening Visit/Visit 1.
- 4. Subject has had a previous response (at any time) to either eltrombopag or romiplostim, defined as at least 2 platelet counts $\geq 50 \times 10^9 / L$.
- 5. Subject is willing and able to comply with all aspects of the protocol, including completing the self-administered TSQM.

5.2 Exclusion Criteria

Subjects who meet any of the following criteria will not be eligible to participate:

- 1. Subject is currently receiving chemotherapy or radiation for any form of cancer.
- 2. Subject with conditions that are likely to prevent them from accurately and reliably completing study assessments, including evidence of moderate to severe dementia, and/or severe and progressive medical illness, as determined by the Investigator.
- 3. Any previous avatrombopag use.
- 4. Previous participation in this study; a subject may not re-enroll after prior discontinuation or completion.
- 5. Enrollment in another clinical study with any investigational drug or device within 30 days of Baseline (or 5 half-lives, whichever is longer); however, participation in observational studies within the previous 30 days is permitted.

5.3 Subject and Study Discontinuation

A subject can withdraw from the study, at any time, and for any reason. The standard of care for the subject will not be affected in any way.

If a subject withdraws prematurely from the study, study staff should make every effort to collect the full panel of data scheduled for the Day 90/Early Termination Visit.

The reason for early termination must be documented in the eCRF. Terminated subjects will not be replaced.

5.3.1 Screen Failures

Subjects who sign and date the informed consent form (ICF) but who fail to meet all the inclusion criteria or meet any exclusion criteria are defined as a screen failure.

The following data will be recorded in the eCRF for screen failed subjects:

- ICF signature date
- Demographic information
- AEs that occur after signing the ICF
- Reason for screen failure (e.g., inclusion/exclusion criteria that was not met, etc.)

Subjects may be re-screened with prior approval from the Sponsor.

5.3.2 Early Termination

A subject may be early terminated for any of the following reasons:

- Subject wishes to withdraw consent for any reason.
- Subject non-compliance or unwillingness to comply with the procedures required by the protocol.
- Subject failed to meet inclusion/exclusion criterion.
- Occurrence of any medical condition that exposes the subject to substantial risk and/or does not allow the subject to adhere to the requirements of the protocol.
- Any SAE, clinically significant AE, severe laboratory abnormality, intercurrent illness, or other medical condition which indicates to the Investigator that continued participation in the study is not in the best interest of the subject.
- Investigator discretion.
- Sponsor request.
- Termination of the study by the Sponsor or a regulatory agency.

If a subject is early terminated from the study, the Early Termination procedures (Section 7.4.5) should be performed. Subjects early terminated from the study will not be replaced, regardless of the reason for early termination.

6 STUDY TREATMENT

Avatrombopag doses will be determined by the treating physician in conjunction with the FDA-approved package insert.

6.1 Randomization and Blinding

All subjects enrolled in this study will receive open-label avatrombopag. Therefore, no randomization or blinding is required.

6.2 Avatrombopag Supplies

A sufficient supply of commercially available avatrombopag will be provided to the clinical site. Avatrombopag will be provided as film-coated tablets, with each tablet containing avatrombopag maleate (equivalent to 20 mg avatrombopag) and excipients.

6.3 Avatrombopag Dosage and Administration

Avatrombopag doses will be determined by the treating physician in conjunction with the FDA-approved DOPTELET USPI.

At the Baseline Visit/Visit 2, the clinical site will dispense the number of avatrombopag tablets required for dosing each subject at the discretion of the Investigator, per the subject's standard of care.

6.4 Receipt of Supplies

Upon receipt of the avatrombopag supplies, the pharmacist, or designee, will visually inspect the shipment and verify drug information, quantity, and condition of the avatrombopag received.

6.5 Avatrombopag Storage Conditions

Avatrombopag should be stored in a secure location, in its original packaging, at a controlled room temperature of 20°C to 25°C (68°F to 77°F) and protected from light and moisture. Excursions are permitted to 15°C to 30°C (59°F to 86°F). The storage location must be a locked room with limited access, available to appropriate study personnel only.

6.6 Compliance

Compliance with the Investigator-prescribed avatrombopag dosing regimen will be evaluated through the study drug accountability eCRF page and the completion of a Dosing Diary by the subject.

The first dose of avatrombopag will be taken while the subject is at the site during the Baseline Visit/Visit 2. During this visit, subjects will be provided with instructions on appropriate at-home avatrombopag administration. When taking avatrombopag at home, subjects should record the date and time of each dose in the provided Dosing Diary.

6.7 Avatrombopag Accountability

The Sponsor will provide the Investigators with a sufficient amount of avatrombopag to begin enrollment for this study. Sites will be responsible for ordering additional avatrombopag as needed, once subjects have been enrolled, via a website (detailed instructions will be provided). It is the responsibility of the Investigator to ensure that a current record of inventory/drug accountability is maintained. Inventory records must be readily available for inspection by the study Clinical Research Associate (CRA), the Sponsor (or designee), or regulatory authorities.

6.8 Avatrombopag Handling and Returns

Upon completion or termination of the study, and upon written authorization from the Sponsor, or its designee, unused and/or partially used avatrombopag should be returned or destroyed at the investigational site. If avatrombopag will be destroyed by the study site, it is the Investigator's responsibility to ensure that the Sponsor or its designee has provided written authorization for proper disposal of avatrombopag, and that appropriate records of the disposal are documented and maintained. No unused avatrombopag may be disposed of until fully accounted for by the Sponsor, or designee.

7 STUDY PROCEDURES

The only protocol-mandated visits are the Screening Visit/Visit 1, the Baseline Visit/Visit 2 (which may be combined with the Screening Visit/Visit 1), Day 15, Day 30, Day 60, and the Day 90/Early Termination Visit.

Data will be collected from information routinely recorded in a subject's medical record and from laboratory data. Except for the Screening Visit/Visit 1, Baseline Visit/Visit 2, Day 15, Day 30, Day 60, and Day 90/Early Termination Visit, no visits, examinations, laboratory tests, or procedures are mandated or recommended as part of this study. All platelet counts collected per the subject's standard of care while the subject is enrolled in the study should be recorded in the eCRF.

A schedule of events in tabular format is provided in Table 2 in Appendix A.

7.1 Informed Consent

Prior to conducting any study-related data collection, informed consent must be signed and dated by the subject. See Section 12.4 for additional information on informed consent.

7.2 Screening Visit (Visit 1)

The Screening Visit/Visit 1 must be completed within 28 days of the Baseline Visit/Visit 2, however, this visit may also be combined with the Baseline Visit/Visit 2.

The following procedures should be performed at the Screening Visit/Visit 1.

- Collect signed and dated informed consent prior to any other study procedures.
- Review of inclusion/exclusion criteria (Section 5) to confirm study eligibility.
- Record subject demographic information including race/ethnicity, date of birth and gender.
- Record ITP history that is available in the subject's medical record, including:
 - o Date of ITP diagnosis.
 - o Number of platelet transfusions in the previous 1 year, including date of last platelet transfusion.
 - Number of previous hospitalizations for ITP.
 - \circ Number of previous significant bleeding events (e.g., blood loss $\geq 1/2$ cup).
 - Most recent dose level and duration of previous treatments with eltrombopag and/or romiplostim, including qualifying eltrombopag/romiplostim treatment over the 90 days prior to study entry.
 - Other previous treatments for ITP, including duration.
 - O History of splenectomy (yes/no).
 - History of thromboembolic events.
- Record the reason for switching to avatrombopag from eltrombopag or romiplostim.

- Record subject-reported responses to brief questions (to be provided) regarding the prior administration of eltrombopag or romiplostim.
- Record any data on Additional Safety Information (Section 9.1.1) or (AESIs) (Section 9.5) that have occurred since the subject signed the ICF.
- Record any AEs that have occurred since the subject signed the ICF.
- Record any concomitant medication use, including concomitant ITP medications.
- Instruct subject on when to return for the Baseline Visit/Visit 2 if the Screening Visit/Visit 1 will not be combined with the Baseline Visit/Visit 2.

7.3 Baseline Visit (Visit 2/Day 1)

The Baseline Visit/Visit 2 must be completed within 28 days of the Screening Visit/Visit 1 but may also be combined with the Screening Visit/Visit 1. If the Baseline Visit/Visit 2 will be combined with the Screening Visit/Visit 1, ensure all procedures listed under Section 7.2 are completed.

The following procedures should be performed at the Baseline Visit/Visit 2.

- Review of inclusion/exclusion criteria (Section 5) to confirm continued study eligibility.
- Administer the TSQM Version 1.4 to the subject prior to any other study procedures.
- Perform World Health Organization (WHO) Bleeding Scale Assessment (Appendix B). The Investigator should ask the subject the following question: "Have you had any bleeding or bruising within the last 7 days?". This assessment should be completed after the TSQM has been completed, but prior to other visit assessments.
- Record any changes in ITP history, including changes in:
 - o Number of platelet transfusions in the previous 1 year, including date of last platelet transfusion.
 - o Number of previous hospitalizations for ITP.
 - o Number of previous significant bleeding events (e.g., blood loss $\geq 1/2$ cup).
 - Most recent dose level and duration of previous treatments with eltrombopag and/or romiplostim, including qualifying eltrombopag/romiplostim treatment over the 90 days prior to study entry.
 - o Other previous treatments for ITP, including duration.
 - o History of splenectomy (yes/no).
 - History of thromboembolic events.
- Record the reason for switching to avatrombopag from eltrombopag or romiplostim.
- Record the date of the last dose of eltrombopag or romiplostim.
- Collect and record platelet count (local lab).
- Determine appropriate dose of avatrombopag, based on instructions in the USPI.

- Administer first dose of avatrombopag, on a full stomach, while the subject is in the clinic and record the date/time of the first dose on the eCRF and on the Dosing Diary.
- Provide instructions to the subject for proper at-home administration of avatrombopag, including completion of the Dosing Diary.
- Dispense avatrombopag and the Dosing Diary to the subject.
- Record any data on Additional Safety Information (Section 9.1.1) or AESIs (Section 9.5) that have occurred since the subject signed the ICF.
- Record any AEs that have occurred since the subject signed the ICF.
- Record any concomitant medication use, including concomitant ITP medications.
- Instruct subject on when to return for the Day 15 Visit.

7.4 Treatment Period (through Day 90)

7.4.1 Day 15 (± 2 Days)/Visit 3

- Perform WHO Bleeding Scale Assessment (Appendix B). The Investigator should ask the subject the following question: "Have you had any bleeding or bruising since I saw you last?". This assessment should be completed prior to other visit assessments.
- Collect and record platelet count (local lab).
- Record the occurrence of any platelet transfusion (including the number of units).
- Record whether the subject required any rescue procedure for bleeding.
- Review subject Dosing Diary and record any deviations from prescribed dosing regimen in the eCRF.
- Record any changes in avatrombopag dose and dose frequency.
- Dispense additional avatrombopag to the subject, as needed.
- Record any data on Additional Safety Information (Section 9.1.1) or AESIs (Section 9.5) that have occurred.
- Record any AEs.
- Record any concomitant medication use, including concomitant ITP medications.
- Instruct subject on when to return for the Day 30 Visit.

7.4.2 Day 30 (± 2 Days)/Visit 4

- Administer TSQM Version 1.4 to the subject.
- Perform WHO Bleeding Scale Assessment (Appendix B). The Investigator should ask the subject the following question: "Have you had any bleeding or bruising since I saw you last?". This assessment should be completed prior to other visit assessments.
- Collect and record platelet count (local lab).

- Record the occurrence of any platelet transfusion (including the number of units).
- Record whether the subject required any rescue procedure for bleeding.
- Review subject Dosing Diary and record any deviations from prescribed dosing regimen in the eCRF.
- Record any changes in avatrombopag dose and dose frequency.
- Dispense additional avatrombopag to the subject, as needed.
- Record any data on Additional Safety Information (Section 9.1.1) or AESIs (Section 9.5) that have occurred.
- Record any AEs.
- Record any concomitant medication use, including concomitant ITP medications.
- Instruct subject on when to return for the Day 60 visit.

7.4.3 Day $60 (\pm 2 \text{ Days})/\text{Visit } 5$

- Perform WHO Bleeding Scale Assessment (Appendix B). The Investigator should ask the subject the following question: "Have you had any bleeding or bruising since I saw you last?". This assessment should be completed prior to other visit assessments.
- Collect and record platelet count (local lab).
- Record the occurrence of any platelet transfusion (including the number of units).
- Record whether the subject required any rescue procedure for bleeding.
- Review subject Dosing Diary and record any deviations from prescribed dosing regimen in the eCRF.
- Record any changes in avatrombopag dose and dose frequency.
- Dispense additional avatrombopag to the subject, as needed.
- Record any data on Additional Safety Information (Section 9.1.1) or AESIs (Section 9.5) that have occurred.
- Record any AEs.
- Record any concomitant medication use, including concomitant ITP medications.
- Instruct subject on when to return for the Day 90/End of Study Visit.

7.4.4 Standard-of-Care Clinic Visits

If the subject has a clinic visit or laboratory assessment of platelet count that is separate from the protocol-required visits described in Section 7.2 through Section 7.4.3, the following data (if available and collected per the subject's standard-of-care) should be recorded in the eCRF.

- WHO Bleeding Scale Assessment, if collected per the subject's standard-of-care.
- Record any platelet counts that are collected, per the subject's standard of care, while enrolled in the study.

- Record the occurrence of any platelet transfusion (including the number of units).
- Record whether the subject required any rescue procedure for bleeding.
- Record any changes in avatrombopag dose and dose frequency.
- Dispense additional avatrombopag to the subject, as needed.
- Record any data on Additional Safety Information (Section 9.1.1) or AESIs (Section 9.5) that have occurred.
- Record any AEs.
- Record any concomitant medication use, including concomitant ITP medications.

7.4.5 Day 90 (±2 Days)/End of Study/Early Termination Visit/Visit 6

The following procedures should be performed during the Day 90/End of Study/Early Termination Visit.

- Administer TSQM Version 1.4 to the subject.
- Perform WHO Bleeding Scale Assessment (Appendix B). The Investigator should ask the subject the following question: "Have you had any bleeding or bruising since I saw you last?". This assessment should be completed after the TSQM but prior to other visit assessments.
- Collect and record platelet count (local lab).
- Record the occurrence of any platelet transfusion (including the number of units).
- Record whether the subject required any rescue procedure for bleeding.
- Record final avatrombopag dose and dose frequency on the eCRF.
- Review Dosing Diary, record any deviations from prescribe dosing regimen, and collect from the subject.
- Record any data on Additional Safety Information (Section 9.1.1) or AESIs (Section 9.5) that have occurred.
- Record any AEs.
- Record any concomitant medication use, including concomitant ITP medications.
- Discharge subject from the study.

7.5 Early Termination Visit

All subjects who are early terminated from the study prior to the Day 90/End of Study Visit should complete the Day 90/End of Study Visit assessments in Section 7.4.5.

8 STUDY ASSESSMENTS

8.1 Treatment Satisfaction Questionnaire for Medication (TSQM)

The TSQM is a 14-item, validated, self-administered patient reported outcome (PRO) questionnaire that is used to assess treatment satisfaction by analyzing the following 4 domains: effectiveness, side effects, convenience, and global satisfaction (Atkinson, 2004).

The TSQM will be administered to the subject at the Baseline Visit/Visit 2, at Day 30, and at the Day 90/End of Study/Early Termination Visit prior to any study procedures.

8.2 Laboratory Examinations

8.2.1 Platelet Count (Local Lab)

Local laboratory platelet counts will be collected per protocol at the Baseline Visit/Visit 2, Day 15, Day 30, Day 60 and at the Day 90/End of Study/Early Termination Visit. All other platelet counts collected per the subject's standard of care while they are enrolled in the study should be recorded in the eCRF.

8.3 World Health Organization Bleeding Scale

Beginning with the Baseline Visit/Visit 2, the Investigator should assess bleeding using the WHO Bleeding Scale (Appendix B) according to verbal response.

During the Baseline Visit/Visit 2, the following question should be asked: "Have you experienced any bruising or bleeding within the last 7 days?".

At each subsequent visit, the following question should be asked: "Have you experienced any bruising or bleeding since I saw you last?".

This assessment should be completed *after* the TSQM at the Baseline, Day 30, and the Day 90 Visits.

9 SAFETY ASSESSMENTS

The Investigator and any qualified designees are responsible for detecting, documenting, and recording events that meet the definition of an AE or an SAE and remain responsible for following up on AEs that are serious, considered related to study procedures, or that caused the subject to discontinue avatrombopag.

9.1 Adverse Events

An AE is defined as any untoward medical occurrence in a subject administered a pharmaceutical product, which does not necessarily have a causal relationship with this treatment. An AE can therefore be any unfavorable and/or unintended sign (including an abnormal laboratory finding), symptom, or disease temporally associated with the use of an investigational medicinal product. All AEs, including observed or volunteered problems, complaints, or symptoms, are to be recorded on the appropriate eCRF.

AEs will be monitored and documented from the time of informed consent until study participation is complete. Subjects should be instructed to report any AE that they experience to the Investigator. Beginning with the informed consent signature, Investigators should make an assessment for AEs at each visit and record the event on the appropriate AE eCRF. Events associated with disease progression should not be reported as AEs or SAEs. However, if in the Investigator's opinion the disease progression is manifesting in an unusual or uncharacteristic manner, the associated events should be reported as AEs/SAEs, as appropriate.

Wherever possible, a specific disease or syndrome (i.e., diagnosis) rather than individual associated signs and symptoms should be identified by the Investigator and recorded on the eCRF. However, if an observed or reported sign or symptom is not considered a component of a specific disease or syndrome by the Investigator, it should be recorded as a separate AE on the eCRF. Additionally, the condition that led to a medical or surgical procedure (e.g., surgery, endoscopy, tooth extraction, or transfusion) should be recorded as an AE, not the procedure.

Any medical condition already present at Screening should not be reported as an AE unless the medical condition or signs or symptoms present at Screening change in severity, frequency or seriousness at any time during the study. In this case, it should be reported as an AE.

Clinically significant abnormal laboratory or other examination findings that are detected during the study or are present at Screening and significantly worsen during the study should be reported as AEs. The Investigator will exercise his or her medical and scientific judgment in deciding whether an abnormal finding is clinically significant. Clinically significant abnormal laboratory values occurring during the clinical study will be followed until repeat tests return to normal, stabilize, or are no longer clinically significant. Any abnormal test that is determined to be an error does not require reporting as an AE.

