1 INTRODUCTION AND BACKGROUND INFORMATION

1.1 Thrombocytopenia

Platelets originate from megakaryocytes in the bone marrow and are an important component of blood that function to maintain normal hemostasis by helping to control bleeding through aggregating and inducing clot formation in conjunction with blood coagulation factors. In healthy individuals, the average lifespan of platelets is 7 to 10 days, after which they are destroyed and replaced with newly generated platelets from the bone marrow. A normal blood platelet count ranges from $150\times10^9/L$ to $450\times10^9/L$, and patients who have less than $150\times10^9/L$ have the condition known as thrombocytopenia, which is associated with easy or excessive bruising and mild to severe or potentially fatal bleeding.

Thrombopoietin (TPO), the principal physiologic regulator of platelet production, is produced constitutively in the liver, circulates in the bloodstream, and is delivered to the bone marrow, where it stimulates the early development of multiple hematopoietic lineages leading to megakaryocytopoiesis. This results in the production of new platelets by the bone marrow, a process which is directly correlated with plasma TPO levels.

The circulating platelet count in the blood is determined by the rates of platelet production and platelet destruction. Thrombocytopenia can result from decreased platelet production in the bone marrow, increased platelet destruction in the blood (such as from autoantibodies), sequestration of platelets in the spleen, and/or the dilution of platelets following multiple blood transfusions. There are numerous disease states which cause thrombocytopenia, including immune thrombocytopenia (ITP), chronic liver disease (CLD), and chemotherapy-induced thrombocytopenia (CIT).

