9.5 Adverse Events of Special Interest

The Investigator will monitor each subject for clinical and laboratory evidence for pre-defined AESIs throughout their participation in this study. The purpose for specifying these AESI is to enable further characterization of the clinical course and management of these events. An AESI may or may not be the consequence of treatment with avatrombopag.

The AESIs defined in this protocol include:

- Thromboembolic events (any thrombotic or embolic event, whether arterial or venous)
- Bleeding events (any clinically significant blood loss [e.g., WHO Grade 2 or higher]).

These events will be recorded on the AE eCRF page. The Investigator will assess and record any additional information on the AESI in detail on a SAE form (whether or not the event meets seriousness criteria in Section 9.2), to be submitted within 24 hours of awareness of the event. During the course of the study, additional AESIs may be identified by the Sponsor.

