9.2 Adverse Events

Adverse events (AEs) will be coded using MedDRA version 26.1 or later. The coding may be updated according to newly released versions of the dictionary.

Severity of AEs is categorized according to the following categories as entered in the eCRF: Mild, Moderate, Severe.

For investigator determined relationship to study drug, AEs are classified as "Related" or "Not Related".

AEs leading to discontinuation of avatrombopag are AEs where action taken is designated as "Drug Withdrawn" in the eCRF.

Two categories for Adverse Events of Special Interest (AESI) will be summarized and are defined based on terms in Standardized MedDRA Queries (SMQs) from MedDRA v26.1 or later:

1. Thromboembolic events - Any thrombotic or embolic event, whether arterial or venous – SMQ = Embolic and thrombotic events
2. Bleeding Events - Any clinically significant blood loss [e.g., bleeding events with CTCAE grade 3+ (based on AE severity [AESEV]>=3] – SMQ = Haemorrhage terms (excl laboratory terms)

[figure not shown]
TEAEs are defined as AEs occurring on or after the first dose of study treatment. TEAE will be tabulated by System Organ Class (SOC) and Preferred Term (PT) by prior TPO-RA (romiplostim and eltrombopag) and overall. TEAESI will be tabulated by AESI category and PT. Subjects with more than one TEAE in a SOC or PT will only be counted once per SOC or PT.

An overview summary table will include the number and percentage of all enrolled subjects with at least one:

- TEAE
- Serious TEAE
- TEAE of special interest (thromboembolic events and bleeding events)
- TEAE related to avatrombopag
- Severe TEAEs
- TEAE leading to study drug discontinuation

Summary tables of TEAEs will be provided for:

- TEAE (by SOC and PT)
- Serious TEAE (by SOC and PT)
- TEAE of special interest (by AESI category and PT)
- TEAE related to avatrombopag (by SOC and PT)

- Severe TEAEs (by SOC and PT)
- TEAE leading to study drug discontinuation (by SOC and PT)

Summary tables will also include number of events for each AE by SOC and by PT.

Listings of all adverse events reported after the consent form is signed (both TEAE and non-TEAE) will be provided and will include information such as the patient identifier, SOC, PT, reported term, date of onset/stop, duration of the event, TEAE, seriousness, severity, action taken, outcome, causality and relationship. A flag will be included in the listings to designate whether an adverse event is treatment-emergent.

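### Protocol 9.1 keeps disease-progression events out of AE and SAE reporting, Protocol 9.5 requires significant bleeding to be recorded as an AE, and nothing says which rule prevails

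*Protocol*

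**What the plan says.** Protocol 9.1 (Adverse Events) contains an exclusion: "Events associated with disease progression should not be reported as AEs or SAEs". It is lifted only at the investigator's discretion: "if in the Investigator's opinion the disease progression is manifesting in an unusual or uncharacteristic manner, the associated events should be reported as AEs/SAEs". Disease progression is not defined for ITP, and bleeding is neither named in the exclusion nor protected from it.

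Protocol 9.5 (Adverse Events of Special Interest) lists two AESI categories, one of which is "Bleeding events (any clinically significant blood loss [e.g., WHO Grade 2 or higher". On where they go, it says: "These events will be recorded on the AE eCRF page". Details are also due on an SAE form within 24 hours of awareness, whether or not the event is serious. Cause is not a condition: "An AESI may or may not be the consequence of treatment with avatrombopag".

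The primary endpoint is the occurrence of AEs and SAEs (Protocol 3.1, SAP 3.2.1). SAP 9.2 summarises treatment-emergent AEs, serious AEs and AESIs from the AE data. Bleeding AESIs are found by a MedDRA query, "SMQ = Haemorrhage terms (excl laboratory terms").

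Bleeding is also graded on the WHO Bleeding Scale from Baseline onward (Protocol 8.3) and tabulated separately (SAP 9.3.2).

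**The concern.** In this population an ordinary bleed can be taken for the disease itself. Protocol 1.1 describes a low platelet count as a condition "which is associated with easy or excessive bruising and mild to severe or potentially fatal bleeding". A site that sees platelets fall after the switch and a characteristic bleed follow has some basis for calling this disease progression. Section 9.1 then tells it not to report the event, while 9.5 tells it to record the event if it is clinically significant.

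The primary endpoint counts whatever is entered on the AE page. If entry depends on which sentence a site follows, the same bleed can count at one site and not at another. The effect on the count has one sign, because the exclusion can only remove events. Loss of platelet control with bleeding is also a central safety question when patients change TPO-RA, so the events at risk of omission matter to the study's main objective.

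**Working it through.** The plan gives no figure on this point, so there is none to reproduce. Its one design calculation, 83% power for TSQM convenience, is unaffected. The check is a comparison of the rules.

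**Step 1. Apply the rules to four kinds of bleed.**

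| Event | 9.1 exclusion | Rule pulling the other way | Result |
|---|---|---|---|
| WHO Grade 2 or higher, typical of ITP, site calls it progression | Do not report | 9.5: AE page and SAE form | Direct conflict |
| Below the 9.5 threshold (e.g. Grade 1, petechial, Appendix B), typical of ITP, site calls it progression | Do not report | None in 9.5 | May be omitted |
| Any bleed the investigator finds unusual | Exclusion lifted | Not needed | Reported |
| Bleed leading to transfusion, site calls it progression | Do not report | 9.1: "the condition that led to a medical or surgical procedure (e.g., surgery, endoscopy, tooth extraction, or transfusion) should be recorded as an AE" | Conflict within 9.1 |

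**Step 2. Look for a rule of precedence.** Sections 9.1 and 9.5 do not refer to each other. Section 9.2 defines seriousness without mentioning progression, and 9.4.1 requires all SAEs to be reported regardless of cause, but neither withdraws the 9.1 sentence, which covers SAEs by name. Section 9.1 also makes a condition present at Screening an AE if it worsens. ITP is present at Screening in every subject, so this rule pulls against the exclusion too. Section 9.1.1 separately collects rebound effects and unusual exacerbation of existing disease, which leaves typical exacerbation outside.

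**Step 3. Trace an omitted bleed through the SAP.** The tables in SAP 9.2 start from AE records. A bleed with no AE record has no preferred term for the haemorrhage query to find, no seriousness flag and no causality assessment. It is therefore absent from the TEAE, serious TEAE and AESI tables.

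**Step 4. See what remains.** The WHO grade is still tabulated by visit and as the worst grade overall, by prior TPO-RA (SAP 9.3.2). Platelet transfusions (SAP 9.3.1) and rescue medication for bleeding (SAP 7) are summarised as well. None of these feeds the AE/SAE endpoint, and the SAP plans no comparison of WHO grades with AE records.

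**Step 5. Size.** If B reportable bleeds occur and a share f is left off as progression, the AE page holds B × (1 − f). The documents give neither B nor f. With f free between 0 and 1, the recorded count lies anywhere between B and 0, so only the direction can be stated.

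A separate matter, not settled here, is that SAP 9.2 illustrates significant bleeding by AE severity of 3 or more, whereas Protocol 9.5 uses WHO Grade 2 or higher.

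**The case against.** The best defence is that 9.5 is the specific, mandatory rule for named events and the 9.1 sentence is general. A careful site would follow 9.5 and record every bleed of Grade 2 or higher. The documents also never call a bleed disease progression: Protocol 1.2 stages ITP by duration and speaks of insufficient response to treatment. Other rules bring events back in: worsening of a condition present at Screening and the condition behind a transfusion (9.1), clinically significant laboratory findings (9.1), and rebound or unusual exacerbation (9.1.1). Bleeding is visible in the WHO, transfusion and rescue outputs, and the protocol already provides for data validation (11.1.5) and monitor review for consistency (12.5).

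Much of this stands, and it limits the point in three ways.

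- A reader might infer that serious bleeds will not reach the sponsor within 24 hours. The documents do not support that. Section 9.5 demands an SAE form in that time, so a late report arises only where a site lets 9.1 override it.
- A reader might try to size the loss from Protocol Table 1, where contusion (26%), epistaxis (19%), gingival bleeding (13%) and petechiae (11%) were counted as AEs. Those rates carry no WHO grade and come from a median of 7 months of avatrombopag, against 90 days here. No document says what share a site would withhold.
- A reader might extend the worry to thromboembolic events. Nothing suggests that these would be read as ITP progression.

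Two parts do not stand. The protocol never says that the specific rule beats the general one, and that argument offers nothing for bleeding below the 9.5 threshold. The general validation and monitoring provisions do not name a WHO-to-AE comparison.

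**Conclusion.** The point holds as a conflict between rules: wrong as written, severity should-fix. Bleeds can be lost to the primary AE/SAE endpoint and to the AE-based AESI tables, but the text does not show that they will be. The conclusion rests on one assumption, that some sites will read a typical ITP bleed as disease progression. The undefined term permits that reading but does not compel it.

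The frequency is unknown and the direction is towards understated AE and SAE counts. It would be too strong to say that bleeding is lost to the study, because the WHO scale still captures it. The omission would also weaken any comparison with Table 1, where bleeding terms were counted as AEs.

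**What to change.** **Protocol.** Reconcile 9.1 with 9.5 by stating that the disease-progression exemption does not apply to bleeding events, to AESIs, or to events meeting a seriousness criterion. One sentence in 9.1 with a cross-reference to 9.5 is enough. Thromboembolic events need no item of their own, since they are already AESIs.

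**SAP.** Add a pre-lock listing of every post-baseline WHO Grade 2 or higher assessment with no matching AE record, and query each one with the site. Because the WHO question covers the time since the last visit, a match can be defined as a bleeding AE with onset, or still ongoing, in that interval. The listing uses data already collected and still works if enrolment has ended. It will not recover bleeding below Grade 2, for which the protocol sentence is the only remedy.

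**Cost.** One clarifying sentence, one listing and a few more queries. AE and SAE counts may rise slightly. The change concerns recording only and touches no dose or treatment rule.
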